17 PATIENT COUNSELING INFORMATION

Inform patients to report:

- Early signs of hypersensitivity reactions including hives, generalized urticaria, tightness of the chest, wheezing, hypotension, or anaphylaxis.
- Development of edema or volume overload including shortness of breath or breathing difficulties

Remind patients that Octaplas is made from human blood and may contain infectious agents that can cause disease. Report flu-like or other symptoms or viral infection.

Manufactured by:

Octapharma Pharmazeutika Produktionsges.m.b.H.
[name]
[name]

Octapharma AB
[name]
[name]

U.S. License No. 1646

Distributed by:

Octapharma USA Inc.
[name]
[name]

Due to the complex and highly variable and individual medical circumstances and interventions that are to be expected in this study, no single parameter or measurement of outcome is chosen as the primary endpoint. All data collected will be summarized and presented descriptively to facilitate the review of population homogeneity and general patterns within and between patients of similar baseline characteristics or disease patterns. No confirmatory hypothesis testing is planned. Any p-value or confidence interval presented is to be understood in the exploratory sense.

The structure and content of this SAP provides sufficient detail to meet the requirements identified by the FDA and International Conference on Harmonization (ICH) of Technical Requirements for Registration of Pharmaceuticals for Human Use: Guidance on Statistical Principles in Clinical Trials¹.

The following documents were reviewed in preparation of this SAP:

- Clinical Study Protocol LAS-212, Version 10 (29-Nov-2017)

The reader of this SAP is encouraged to also read the clinical protocol for details on the planned conduct of this study. Operational aspects related to collection and timing of planned clinical assessments are not repeated in this SAP unless relevant to the planned analyses.

¹ International Conference on Harmonization. (1998). Guidance on Statistical Principles. ICH Topic E9 (Statistical Principles for Clinical Trials). London: International Conference on Harmonization.

2. Purpose

This SAP outlines all statistical analyses to be performed on data collected in study LAS-212, and the resulting output that will be compiled to support the completion of the Clinical Study Report (CSR).

The planned analyses identified in this SAP will be included in regulatory submissions and/or future manuscripts. Exploratory analyses not necessarily identified in this SAP may be performed to support the clinical development program. Any post-hoc or unplanned analyses performed that are not identified in this SAP will be clearly identified in the respective CSR.

The statistical output provided to the medical writer of the CSR will closely follow the ICH guideline for industry on topic E3 (Structure and Content of Clinical Study Reports²) to facilitate the subsequent compilation of the CSR.

This statistical output will consist of tables, figures and listings, including

- Tables, figures and listings used or referenced in, or appended to the CSR as detailed in the remainder of this SAP (section 14 of the CSR)
 - Demographic data summary figures and tables
 - Efficacy data summary figures and tables
 - Safety data summary figures and tables
- Listings provided as appendices to the CSR
 - Patient data listings (section 16.2 of the CSR)
 - Individual patient data listings (section 16.4 of the CSR) will be covered by inclusion of SAS datasets into the electronic submission to the authorities

A detailed list of all tables, figures and listings (TFLs) will be supplied in a separate document later when all feedback from authorities will be available.

² International Conference on Harmonization. (1996). Guideline for Industry. ICH Topic E3 (Structure and Content of Clinical Study Reports). London: International Conference on Harmonization.

3. Study Objectives and Endpoints

3.1. Study Objectives

3.1.1. Primary Objectives

The primary objective of the study is to assess the safety and tolerability of Octaplas in the pediatric population by monitoring serious adverse events (SAEs), adverse drug reactions (ADRs), thrombotic events (TEs), thromboembolic events (TEEs) and hyperfibrinolytic events, including laboratory parameters for metabolic derangements, renal function, and hematologic implications.

3.1.2. Secondary Objectives

The secondary objective is to assess the efficacy of Octaplas in the pediatric population by measuring hemostatic parameter improvements reflecting changes in hemostasis.

3.2. Study Endpoints (Target Variables)

3.2.1. Primary Endpoints

The primary (safety) endpoints are:

- Incidence of SAEs, ADRs (e.g., allergic reactions), TEs, TEEs and hyperfibrinolytic events, beginning after the start of the first infusion episode until the final examination (end of safety follow-up period).
- Clinically significant changes in laboratory parameters to assess for metabolic derangements, renal function, and hematologic implications as measured by the following: Chem 7 (metabolic panel), complete blood count (CBC), calcium and ionized calcium.

3.2.2. Secondary Endpoints

The secondary endpoints are:

- Clinically significant changes in hemostatic parameters as measured by the following: international normalized ratio (INR), prothrombin time (PT), activated partial thromboplastin time (aPTT), thromboelastography (TEG) or thromboelastometry (ROTEM).
- Volume (dose in mL/kg) of Octaplas used per infusion episode for each patient.
- Medically significant changes in vital signs
- Investigator's assessment of overall safety observed for each patient.

4. Study Methods

4.1. Overall Study Design and Plan

Study LAS-212 is designed as an open-label, multicenter, post-marketing requirement (PMR) phase IV study. Therefore no randomization or blinding procedures are performed.

This study will enroll a total of 50 pediatric patients from 0 to ≤ 16 years of age with acquired deficiencies due to liver disease and/or in pediatric patients requiring cardiac surgery or liver surgery who require replacement of multiple coagulation factors. The substitution of coagulation factors is also applicable for young children who require cardiac surgery and require priming of the cardiopulmonary by-pass circuit due to the dilution of the increased volume of the by-pass circuit relative to the circulating blood volume of the child.

The study infusion(s) of Octaplas will occur over a maximum 72-hour treatment period. The number of infusion episodes³ and the actual total volume (dose in mL/kg) of Octaplas administered to a patient within the 72-hour treatment period will depend on the clinical setting and physician discretion. Each infusion dose will be at least 10mL/kg or one unit (unless a lesser dose is medically justified) and administered at a rate that should not exceed 0.020-0.025 mmol citrate per minute, which is equal to Octaplas per kg per minute. This limitation is not applicable for devices used for cardiopulmonary bypass or extracorporeal membrane oxygenation or similar. In case situations like e.g. a serious hemorrhage necessitates a rapid infusion ≥ 1 mL/kg and the benefits outweigh the potential risks, the infusion speed can be ≥ 1 mL/kg body weight.

After 72 hours (maximum duration) from the start of the first infusion of Octaplas, the study treatment period will end. Patients will be monitored for SAEs, ADRs, TEs, TEEs and hyperfibrinolytic events for 72 (± 6) hours after the last Octaplas transfusion is completed (72-hour Safety Follow-up Period).

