Name of Active Ingredient: Human Coagulation Active Plasma For Infusion, S/D treated	Date of Final Protocol: 19-Nov-2016

prior to enrollment if it was not previously performed during the current hospital admission. Female patients of childbearing potential are excluded from the study if the pregnancy test is positive. Per physician discretion, he/she will decide if clinical indication for a plasma infusion is necessary and will place the plasma order accordingly. The type of surgical procedure indicated and important operative interventions will also be recorded. Patients determined to have a reasonable probability to receive intra-operative plasma transfusion according to the Investigator's clinical judgment may also be approached for consent to participate. If these patients are subsequently not prescribed plasma intra-operatively or postoperatively they will be determined to be a screening failure and not included in the analysis.
 
Pre-Infusion: Within 6 hours prior the start of the first infusion episode, vital signs and several laboratory tests will be assessed to measure metabolic derangements and renal function.
 
72-hour Study Treatment Period: The number of infusion episodes¹ and actual total volume (dose in mL/kg) of Octaplas administered to a patient within the 72-hour treatment period will depend on the clinical setting and physician discretion. The infusion rate of Octaplas should not exceed 0.020-0.025 mmol citrate per minute, which is equal to Octaplas per kg per minute. This limitation is not applicable for devices used for cardiopulmonary bypass or extracorporeal membrane oxygenation or similar. In case situations like e.g. a serious hemorrhage necessitates a rapid infusion $\geq 1\text{mL/kg}$ and the benefits outweigh the potential risks, the infusion speed can be $\geq 1\text{mL/kg}$ body weight. The first infusion dose will be at a minimum of 10 mL/kg or one unit unless a lesser dose is medically justified. If infusion episodes are performed and the dose administered is less than 10 mL/kg, the medical reason justifying this dosage will be recorded in the case report form (CRF), since at least 10 mL/kg are required to significantly increase the respective plasma protein levels.
 
Post-infusion episode samples should be drawn within 30 to 60 minutes after each infusion episode. If the patient requires priming of the cardiopulmonary bypass (CPB) circuit with plasma, the post-infusion episode samples should be drawn 30-60 minutes after reversal of heparin during the process of coming off CPB. For the first infusion episode it is mandatory that pre- and post-infusion episode samples for hemostatic and
	

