5.4 Dose and Dosing Schedule

The actual volume of Octaplas administered to a patient will depend on the clinical setting.

If the time interval between the end of one Octaplas infusion and the beginning of the next Octaplas infusion is no longer than 60 minutes, then this will be regarded as 1 infusion episode. If the time interval is more than 60 minutes, this will be counted as 2 different infusion episodes. For patients on CPB who are primed with plasma, a transfusion episode will begin with the initiation of the circuit with plasma and will end when the heparin is reversed during the process of coming off CPB.

The infusion rate of Octaplas should not exceed 0.020-0.025 mmol citrate per kilogram per minute, which is equal to <1 mL Octaplas per kg per minute. This limitation is not applicable for devices used for cardiopulmonary bypass or extracorporeal membrane oxygenation or similar. In case situations like e.g. a serious hemorrhage necessitates a rapid infusion ≥ 1 mL/kg and the benefits outweigh the potential risks, the infusion speed can be ≥ 1 mL/kg body weight. The dose (mL) of Octaplas to be infused will depend on the age and BW of the patient. The first infusion dose will be at a minimum of 10 mL/kg or one unit unless a lesser dose is medically justified. If infusions are performed and the dose administered is less than 10 mL/kg the medical reason justifying this dosage will be recorded in the CRF, since at least 10 mL/kg are required to significantly increase the respective plasma protein levels

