5.5 Citrate Toxicity

Citrate toxicity can occur with volumes exceeding one milliliter of Octaplas per kg per minute. The infusion rate should not exceed 0.020-0.025 mmol citrate per kilogram per minute (i.e., less than one milliliter Octaplas per kg per minute). Symptoms attributable to citrate toxicity (hypocalcaemia) include e.g., fatigue, paresthesia and muscle spasms, especially in patients with liver function disorders. Administer calcium gluconate intravenously into another vein in order to minimize citrate toxicity.

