9.4. Measurement of Treatment Compliance

The following parameters will be listed and/or summarized per patient and/or per infusion:

- Body weight
- Actual dose (total and per kg body weight, based on the latest available weight measurement)

- Total dose of Octaplas administered
- Total number of infusions administered
- Total number of bags and total volume of solution administered
- Infusion times and rates (mL/kg/min)
- Overall amount of product administered and batches used (only included in data listings)

During ongoing medical review it was noted that particular infusion patterns associated with cardiac surgeries due to the use of bypass circulation devices in clinical practice were not foreseen beforehand. To account for this the following categorization will be introduced for the analysis of infusion speed and dosing:

- Normal infusion
- Bypass priming
- Bypass warming up

10. Efficacy Analysis

This study will examine the efficacy of Octaplas by measuring hemostatic parameter improvements reflecting changes in hemostasis.

The following hemostatic parameters will be assessed: INR, PT, aPTT and TEG with Kaolin activation or ROTEM EXTEM. Pre- and post-infusion episode samples for hemostatic and laboratory parameters will be tested. The pre-infusion episode laboratory samples should be drawn within 6 hours before the start of the first infusion episode and within 60 minutes prior to the start of the subsequent infusion episodes. Post-infusion episode samples should be drawn within 30 to 60 minutes after the end of each infusion episode.

Beside the complete descriptive and graphical presentations of all available parameters as described above (see sections 5.2 and 8), the actual data collected might suggest additional factors that potentially affect the hemostatic parameters after the results from the planned analysis are completed; in this case full details of additional analyses with respect to such covariates will be given in the CSR.

All efficacy endpoints will be presented on basis of both, the FAS and the PP analysis sets, to allow for an assessment of the robustness of the results with respect to protocol violations. The FAS analysis is considered to be the primary assessment of efficacy, and will be presented first in the report.

11. Safety and Tolerability Analyses

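### The citrate infusion-rate limit is per minute in the synopsis and SAP 4.1 but per kilogram per minute, with the same numbers, in Protocol 5.4 and the package insert

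*SAP*

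**What the plan says.** Five places state the limit.

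- **Protocol synopsis, 72-hour treatment period:** "The infusion rate of Octaplas should not exceed 0.020-0.025 mmol citrate per minute, which is equal to Octaplas per kg per minute".
- **SAP 4.1:** the rate "should not exceed 0.020-0.025 mmol citrate per minute, which is equal to Octaplas per kg per minute".
- **Protocol 5.4:** the rate "should not exceed 0.020-0.025 mmol citrate per kilogram per minute, which is equal to <1 mL Octaplas per kg per minute".
- **Package insert, section 5.5 (protocol Appendix 1):** "The infusion rate should not exceed 0.020-0.025 mmol citrate per kilogram per minute", which it explains as less than 1 mL/kg/min.
- **Protocol 1.3:** volume terms only, a maximum of 1 mL/kg/min.

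The synopsis, Protocol 5.4 and SAP 4.1 add that the limit does not apply to bypass, ECMO or similar devices. They also add an exception for situations such as serious hemorrhage, expressed as at least 1 mL/kg with no unit of time.

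SAP 9.4 lists or summarizes infusion rates in mL/kg/min, split into normal infusion, bypass priming and bypass warming up. SAP section 7 names dosing errors among the deviations that may be considered for exclusion from the per-protocol set.

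**The concern.** The same pair of numbers carries two different units. A limit in mmol per minute is one total for every patient, whereas a limit in mmol per kilogram per minute grows with body weight. The study enrolls from birth to 16 years, so the gap between the two is not constant but varies with each child's weight. The synopsis and SAP sentence also does not agree with itself: it sets an absolute citrate rate equal to a rate per kilogram.

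This is a stated administration limit tied to citrate toxicity, and ionized calcium is one of the primary endpoint parameters. It is also the only numeric rate limit in the SAP. Anyone judging a reported rate, or deciding whether an infusion was a dosing error, needs to know which text is the reference. The rapid-infusion exception cannot be applied as a rate at all, because a volume per kilogram without a time is not a rate.

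**Working it through.** **Inputs**

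- Citrate limit: 0.020-0.025 mmol, per minute (synopsis, SAP 4.1) or per kilogram per minute (Protocol 5.4, package insert 5.5).
- Sodium citrate dihydrate: 0.88-1.48 g per 200 mL bag (Protocol 5.2; package insert section 11).
- Molar mass of sodium citrate dihydrate: 294.10 g/mol. This is a chemical constant and is not in the documents.
- Dose for illustration: 10 mL/kg, the figure in Protocol 5.4.
- Body weights of 3, 10 and 50 kg. These are assumptions; the documents give none.

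**Step 1: citrate concentration**

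Concentration = g per bag / 294.10 x 1000 / 200 mL.

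- Lower content: 0.88 / 294.10 x 1000 / 200 = 0.0150 mmol/mL.
- Upper content: 1.48 / 294.10 x 1000 / 200 = 0.0252 mmol/mL.

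**Step 2: reproduce the protocol's own equivalence**

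Volume rate = citrate limit / concentration. At the upper content, 0.020 / 0.02516 = 0.79 and 0.025 / 0.02516 = 0.99 mL/kg/min. This reproduces the statement in Protocol 5.4 that the per-kilogram limit means less than 1 mL/kg/min. At the lower content the same division gives 1.34-1.67 mL/kg/min, so the stated equivalence is the high-citrate case. The working below therefore uses the upper content.

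**Step 3: ratio of the two texts**

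(limit per kg x weight) / limit = weight in kg. This is exact and does not depend on citrate content.

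**Step 4: size at the upper citrate content**

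Read literally, the per-minute text allows 0.79-0.99 mL/min in total at any weight. Minimum time for 10 mL/kg = 10 x weight / total volume rate. For 10 kg: 100 / 0.994 = 101 min and 100 / 0.795 = 126 min. Under the per-kilogram text: 10 / 0.994 = 10 min and 10 / 0.795 = 13 min at any weight.

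| Assumed weight | Citrate limit, per-kg text (mmol/min) | Citrate limit, literal per-minute text (mmol/min) | Ratio | Least time for 10 mL/kg, per-kg text | Least time for 10 mL/kg, literal text |
|---|---|---|---|---|---|
| 3 kg | 0.060-0.075 | 0.020-0.025 | 3 | 10-13 min | 30-38 min |
| 10 kg | 0.20-0.25 | 0.020-0.025 | 10 | 10-13 min | 101-126 min |
| 50 kg | 1.00-1.25 | 0.020-0.025 | 50 | 10-13 min | 503-629 min (8.4-10.5 h) |

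**Step 5: sensitivity to citrate content**

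At the lower content the literal text gives 60-75 min for the 10 kg child (100 / 1.671 and 100 / 1.337). The citrate figure in Protocol 5.4 alone would then allow more than 1 mL/kg/min, but that section also states less than 1 mL/kg/min, so 10 mL/kg still takes more than 10 min under it. The gap in time is then about 6- to 7.5-fold rather than tenfold.

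**The case against.** **The meaning can be inferred.** The defective sentence ends in a per-kilogram rate, Protocol 1.3 uses mL/kg/min, Protocol 5.5 says the product is used according to its labeling, and the SAP sends readers to the protocol for study conduct. This stands as a reason to expect that few readers would apply the literal figure. It does not make the text correct, and an administration limit should not have to be inferred.

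**It may be lost text.** That could well explain the gap before the product name, where a symbol and a volume seem to be missing, and nothing here rests on that gap. It does not readily explain ordinary words missing in two separate documents.

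**The SAP was written from a later protocol.** It cites Version 10 of 29-Nov-2017, while the supplied protocol is dated 19-Nov-2016. Even so, the synopsis and section 5.4 conflict within the supplied protocol.

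**No analysis computes from the limit.** This stands. SAP 9.4 summarizes rates without a threshold, safety is analyzed on the safety population, the full analysis set is primary for efficacy, and per-protocol exclusions are decided case by case by a panel.

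A reader might also infer more than the documents support:

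- *That the SAP text allows infusion that is too fast.* The reverse is true: read literally, it is the more restrictive text above 1 kg.
- *That nearly all infusions would be classified differently.* The documents give no expected infusion rates. A slow infusion in a small infant could satisfy both texts, and bypass and ECMO devices are exempt.
- *That the per-kilogram text permits up to 1.67 mL/kg/min, or 10 mL/kg in 6 minutes.* Both exceed the volume limit that Protocol 5.4 itself states.

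**Conclusion.** The inconsistency is real and should be corrected. The citrate limits in the synopsis and SAP 4.1 on one side, and in Protocol 5.4 and the package insert on the other, differ by exactly the body weight in kg when read as written. At the upper citrate content and an assumed 10 kg, that is a tenfold difference in minimum infusion time. The ratio of the citrate limits rests on no assumption; the times rest on the molar mass, the upper end of the stated citrate range and the illustrative weights.

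The consequence is limited. No primary result, sample size or test depends on the limit. It affects a stated safety limit for administration, and the yardstick for judging reported rates and dosing deviations. The missing time unit in the rapid-infusion exception is a separate defect in the same text and occurs in all three places where the exception appears.

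**What to change.** The sponsor must reconcile the synopsis, Protocol 1.3, Protocol 5.4, the package insert section 5.5 and SAP 4.1 so that one unit is used throughout, and give the rapid-infusion exception a time unit in the synopsis, Protocol 5.4 and SAP 4.1. Which limit applies is for the sponsor to settle, and no rate is proposed here. No new analysis or deviation rule is needed, and no limit is asked for on bypass devices, which the documents exempt. The cost is a wording correction, with any change to the protocol going through the amendment process in Protocol 10.4.

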4.2. Selection of Study Population

The study population consists of pediatric patients of both sexes and ≤ 16 years of age, who require liver or cardiac surgery and/or with liver dysfunction associated with coagulopathy in whom replacement of multiple coagulation factors is required.

It is planned to enroll fifty patients from the following two age categories:

1. Neonates/Infants (0-2 years): a maximum of 37 patients
2. Children > 2 years and ≤ 16 years: a minimum of 13 patients. A full set of baseline characteristics will be collected to allow evaluation and comparison of study outcomes with respect to different patient characteristics as indicated by the data.

³ An infusion episode is defined as any amount of Octaplas infusion given, with no more than 60 minutes break between 2 Octaplas infusions. If the time interval between the end of one Octaplas infusion and the beginning of the next Octaplas infusion is more than 60 minutes this will be counted as 2 different infusion episodes.

5. Sequence of Planned Analyses

5.1. Interim Analyses

No interim analysis is planned.

5.2. Final Analyses and Reporting

Due to the complex and highly variable and individual medical circumstances and interventions that are to be expected in this study, no single parameter or measurement of outcome is chosen as the primary endpoint. All data collected will be summarized and presented descriptively to facilitate the review of population homogeneity and general patterns within and between patients of similar baseline characteristics or disease patterns. No confirmatory hypothesis testing is planned. Any p-value or confidence interval presented is to be understood in the exploratory sense.

To allow a holistic review and interpretation of each course of treatment, all parameters relevant for the assessment of safety will be presented descriptively in full detail, by subgroups of interest as well as in total. The safety assessment will include the occurrence of SAEs, ADRs, TEs, TEEs and hyperfibrinolytic events. To facilitate the detection of any possible safety signal, all these events will be characterized and analyzed by age (\leq and $>$ 2 years of age respectively), underlying diagnosis, seriousness, severity, relation to study drug and timely relationship to study drug administration. In addition to these pre-planned categories, the collected data will be examined to identify additional characteristics of interest such as particular types of surgeries or procedures, relevant concomitant medications, or Standardized MedDRA Queries (SMQs) covering a noticeable number of events. The occurrences of all specific safety events will be presented for all these categories and in total, together with the associated 95% confidence intervals.

The following subgroups/categories were identified during the ongoing medical review, and will be considered in the presentation of safety data as detailed above:

- Underlying Diagnosis
 - Congenital heart disease
 - Liver disease requiring transplant
 - Sepsis related coagulopathy
- Types of surgery
 - Cardiac
 - Orthotopic liver transplant
 - None
- No further characteristics were identified in medical history, concomitant medications or reported AE terms that called for further subgroup analyses.

To account for the abovementioned diversity in the study population, individual patient profiles will be generated, displaying the baseline characteristics as well as all interventions, treatment details and relevant measurements on a time scale. This will facilitate the review of each individual course of treatment by the trial medical monitor or expert to assess the efficacy of the treatment but also to detect any safety signal that might not be reflected in the ADR rates.

Hemostatic parameters will be presented descriptively per time point, including shift tables. Individual courses of hemostatic parameters will be presented graphically as Trellis plots.

Vital sign measurements will be summarized by descriptive statistics, including shift tables. All measurements outside the age-specific thresholds defined in the trial validation plan and/or the TFLs document will be listed and reviewed individually.

All safety laboratory data – absolute values as well as changes from baseline – will be presented descriptively per time point. All measurements outside the age-specific thresholds defined in the trial validation plan and/or the TFLs document will be listed and reviewed individually.

All data will be presented in total as well as in sub-groups reflecting age (\leq and $>$ 2 years), gender, underlying diagnosis, surgical procedures performed as detailed above and to the extent appropriate.

6. Sample Size Determination

The chosen number of 50 pediatric patients is not derived from statistical considerations of power, but to gather enough clinical evidence to obtain a sound and meaningful medical assessment and sufficient safety information in a reasonable amount of time.

